## Immune Tolerance Induction (ITI) (if applicable)

Patients who develop a clinically significant and non-transient FVIII inhibitor will be offered to start ITI with the IMP. Inhibitors that 'disappear' without any clinical signs or symptoms, where no FVIII dosing increase was required, and that turn to <0.6 BU within a period of 6 months after first detection are regarded as "transient".

The modified Bonn Protocol for inhibitor elimination is recommended:

- Low responders (<5 Bethesda Units [BU]) should receive 50-100 IU FVIII/kg BW daily or every second day. In case the inhibitor increases to 5 BU or more, the patient should switch to the high responder regimen.
- High responders ( $\geq$ 5 BU) should receive 100-150 IU FVIII/kg BW every 12 hours.

Once the inhibitor is eliminated (<0.6 BU), the FVIII recovery is  $\geq$ 66% of normal (defined as 1 IU FVIII/kg BW raises the plasma FVIII activity by 1.5%), and the half-life of FVIII is at least 6 hours, a continuous reduction of about 10% of the initial ITI dosage should be initiated, until the patient has reached a prophylactic treatment regimen of 30-50 IU FVIII/kg BW every other day.

Any other ITI approach using Human-cl rhFVIII as the selected FVIII concentrate is possible.

All treatment details and the further development of the inhibitor titre need to be documented.

Patients who do not start ITI within one year after inhibitor detection are withdrawn from the study.

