3.4 Assessment of Objectives

3.4.1 Immunogenicity

The *primary objective* is to investigate the immunogenicity of Human-cl rhFVIII.

The *primary endpoint* is the incidence of inhibitors within the observation period. For one patient an inhibitor is assessed to be positive if the modified Bethesda assay (Nijmegen modification) results in a titer ≥ 0.6 BU at any time point during the observation period.

Inhibitor activity will be determined centrally at the following time points: At baseline (Screening Visit), every 3-4 EDs until ED 20, every 10-12 EDs or every 3 months \pm 2 weeks after ED 20 (whichever comes first), at study completion; at any time in the case of a suspicion of inhibitor development.

In case of a positive inhibitor result, an inhibitor re-testing using a second separately drawn sample should be performed centrally; the result of the second sample will be taken as the final result for the time point. Low titre inhibitors will be defined as ≥ 0.6 to < 5 BU, high-titre inhibitors will be defined as ≥ 5 BU.

Patients who develop a non-transient inhibitor will have an option to start ITI treatment. Patients developing inhibitors and not starting ITI within one year after inhibitor detection will be

withdrawn from the study. Inhibitors that 'disappear' without any clinical signs or symptoms, where no FVIII dosing increase was required, and that turn back to <0.6 BU within a period of 6 months after first detection are regarded as "transient". Patients who develop such a transient inhibitor will continue regular treatment within the study until they have reached ED 100 or a maximum period of 5 years.

Definition of inhibitor confirmation and time to inhibitor occurrence:

Occurrence of inhibitors:

For these definitions inhibitor titres determined in the central laboratory are considered.

(I1) FVIII:C high titre inhibitor occurrence is confirmed, if

inhibitor level ≥ 5 BU at one time point $t_{1,H}$ and

- inhibitor level confirmed to be ≥ 5 BU at a subsequent* time

point $t_{2,H}$ or

- retest of sample from *any* time point $t_{3,H}$ ($=t_{1,H}, t_{2,H}$ or later) confirmed to be ≥ 5 BU.

* 'Subsequent' in the context of this document always means 'at a later time point' or 'in a later sample', but not necessarily the immediate consecutive visit or sample.

(I2) FVIII:C Inhibitor occurrence in a patient is confirmed, if

- a high titre inhibitor is confirmed according to (I1)

or if

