- inhibitor level ≥ 0.6 BU at one time point $t_{1,I}$

and retest of sample from same time point $t_{1,I} \geq 0.6$ BU

and inhibitor level ≥ 0.6 BU at a subsequent time point

or

- inhibitor level ≥ 0.6 BU at one time point $t_{1,I}$

and inhibitor level ≥ 0.6 BU at a subsequent time point

and retest of sample from same time point $t_{2,I} \geq 0.6$ BU

or

- inhibitor level ≥ 0.6 BU at three subsequent time points $t_{1,I}, t_{2,I}$ and $t_{3,I}$
(e.g. if retests are not available).

(I3) An inhibitor is confirmed to be a low titre inhibitor, if

- occurrence of inhibitor of < 5 BU is confirmed (according to I2) but

- occurrence of high titre inhibitor (according to I1) is *never* confirmed during the observation period*

(Note: a low titre inhibitor which turns to a confirmed high titre inhibitor according to definition I1 is solely counted as a high titre inhibitor. Inhibitors initially measured as low titre of < 5 BU and remain low titre (< 5 BU) are defined as low titre inhibitors)

*This condition means that a patient only can be defined as having either a low titre inhibitor or a high titre inhibitor. The patient cannot be counted twice.

These definitions for confirmation of positive inhibitors and for high and low titre inhibitors are considered to be relevant for the overwhelming number of inhibitor occurrences. However, there might be cases where additional information (e.g. when taking the whole sequence of inhibitor testing or additional local lab data into account) may suggest that an inhibitor may be assessed rather high titre than low titre. All inhibitor data will be reviewed during the Data Review Meetings before interim analysis/ final analysis to identify such cases.

Time and number of EDs until inhibitor occurrence:

(I4) The time / number of EDs to inhibitor occurrence is defined

- by the time between ED1 and the date of the first positive inhibitor titre detected in a confirmed

inhibitor patient (I2)

- more exactly : as

minimum {date of $t_{1,H}$, date of $t_{1,I}$ } – date of Day 1 (ED1) (days) ,

or the number of EDs (with injections for any indication) during this time frame (ED1 until day before minimum {date of $t_{1,H}$, date of $t_{1,I}$ })

(Note: If different dates for $t_{1,H}$ and $t_{1,I}$ are available, the earlier date will be taken into account)

Censoring: Time / number of EDs until any inhibitor will be censored for patients without inhibitor at date of last available inhibitor testing

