- Characteristics and amount of other blood products or rescue medication administered at any time prior, during or post the surgical procedure
- Efficacy evaluation by the surgeon at the end of the surgery and by the surgeon and the haematologist on the last post-operative day (end of post-operative phase).

In addition to the four point scale (very good, good, moderate, none), the proportion of surgeries with successful treatment according to the overall efficacy assessment will be presented.

“Successfully treated” are all “excellent” and “good” efficacy ratings of surgical procedures.

Subjects who switch to another FVIII product during a surgery* will be considered treatment failures, i.e. the efficacy will be imputed to be “none” for each haemostatic efficacy assessment after the switch in the efficacy analyses for this surgery

* those surgeries will be excluded from the SURG-PP population.

- These patients may stay in the study until they have reached their regular end of the study
- Expected (average and maximum) and actual blood loss and difference between planned and actual blood loss
- Expected and actual duration of the surgical procedure and difference between expected and actual duration
- Pre-, intra-, and post-operative FVIII plasma levels
- Any wound haematomas and whether they require surgical evacuation
- Laboratory tests: haematology and clinical chemistry (pre- and postoperatively)
- Vital signs (pre- intra- and postoperatively)
- Details on concomitantly administered products including any blood/blood product transfusions but excluding drugs given for routine anaesthesia.

9.5 **On-demand treatment**

Study drug consumption data for on-demand treatment (IU FVIII /kg BW per month, per year; exposure days) per subject and in total (for subjects on prophylactic treatment) will be presented descriptively for subjects receiving on-demand treatment.

9.6 **ITI treatment**

The percentage of subjects under ITI treatment with complete success (inhibitor-free, normalised recovery and half-life; see Chapter 10) of the therapy will be displayed descriptively. Kaplan-Meier curves will show the distribution of the time to complete success.

Study drug consumption data for subjects with ITI treatment (IU FVIII /kg BW per month, per year; exposure days) per subject and in total will be presented descriptively.

9.7 **Resource Use Analysis Plan**

The statistical analysis of resource use parameters will be descriptive.

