14.2.9	T	Statistics on the dosage of Human-cl rhFVIII (IU/kg) for ITI treatment per month, per year, per exposure day, per injection and in total	ITI
14.2.10	T	ITI: Statistics on changes in treatment schedule	ITI
14.2.11	T	ITI: Frequency table on haemostatic agents used under ITI	ITI
14.2.12	T	ITI: Frequency table on number and percentage of finalized ITI therapy (Number of criteria fulfilled and rate of complete successes)	ITI
14.2.13	T	ITI: Frequency table on number and percentage of individual criteria of success fulfilled	ITI
14.2.14	F	ITI: Kaplan Meier curves on time to complete success (any inhibitor, low titre inhibitor, high titre inhibitor)	ITI
		PROPHYLAXIS	
14.2.15	T	Number of exposure days and number of infusions administered for prophylactic treatment with Human-cl rhFVIII	PROPH, PROPH-PP
14.2.16.1	T	Statistics on the number of exposure days for prophylactic treatment to Human-cl rhFVIII and number of dosages administered	PROPH, PROPH-PP
14.2.16.2	T	Statistics on the number of exposure days for prophylactic treatment to Human-cl rhFVIII and number of dosages administered - restricted to subjects assessed to have received continuous prophylaxis	PROPHcont
14.2.17.1	T	Statistics on the amount of Human-cl rhFVIII (IU) for prophylactic treatment per month, per year, per exposure day, per injection and in total	PROPH, PROPH-PP
14.2.17.2.1	T	Statistics on the dosage of Human-cl rhFVIII (IU/kg) for prophylactic treatment per month, per year, per exposure day, per injection and in total	PROPH, PROPH-PP

14.2.17.2.2	T	Statistics on the amount of Human-cl rhFVIII (IU/kg) for prophylactic treatment per month, per year, per exposure day, per injection and in total - restricted to subjects assessed to have received continuous prophylaxis	PROPHcont
14.2.17.2.3	T	Statistics on the amount of Human-cl rhFVIII (IU/kg) for prophylactic treatment during the inhibitor-free period per month, per year, per exposure day, per injection and in total - restricted to subjects assessed to have received continuous prophylaxis	PROPHcont
14.2.18.1	T	Prophylactic Treatment (dose changes and interruptions of prophylactic treatment)	PROPH, PROPH-PP
14.2.18.2	T	Prophylactic Treatment: Frequency table on haemostatic agents used under prophylactic treatment	PROPH, PROPH-PP
14.2.19.1.1 .1	T	Overall Efficacy Assessment of Prophylactic Treatment (Rate of BEs with 95% confidence interval) – Spontaneous BEs	PROPH, PROPH-PP

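### The ITI success curves by titre (Figure 14.2.14) would be sorted by a class that uses titres measured during ITI, which tilts them in favour of low titre; the class should be fixed at the first ITI dose.

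*SAP*

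**What the plan says.** **The output.** SAP section 13 lists Figure 14.2.14 for the ITI population as "ITI: Kaplan Meier curves on time to complete success (any inhibitor, low titre inhibitor, high titre inhibitor"). SAP 9.6 adds only that "Kaplan-Meier curves will show the distribution of the time to complete success". Neither place states the time origin, the censoring rule or the date at which titre class is set.

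**The class rule.** The only rules that assign patients to low or high titre are I1-I3 in SAP 3.4.1.
- I3 calls an inhibitor low titre only if "occurrence of high titre inhibitor (according to I1) is *never* confirmed during the observation period".
- A note adds that "a low titre inhibitor which turns to a confirmed high titre inhibitor according to definition I1 is solely counted as a high titre inhibitor", and a footnote that "a patient only can be defined as having either a low titre inhibitor or a high titre inhibitor".
- On the data source: "For these definitions inhibitor titres determined in the central laboratory are considered".
- Data review may override the rule where further information "may suggest that an inhibitor may be assessed rather high titre than low titre". Only that direction is described.

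**ITI in the observation period.** Protocol 6.2.2 treats the end of the planned observation period and the Completion Visit as the same event. Protocol 6.1.2 places that visit after ITI for ITI patients. Titre testing on ITI is planned bi-weekly at first and monthly to 3-monthly later (protocol 6.1.2), and Table 8 has a central-laboratory inhibitor screen in its ITI column.

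**Rises on ITI.** Protocol 5.4 foresees them in low responders: "In case the inhibitor increases to 5 BU or more, the patient should switch to the high responder regimen".

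**The concern.** A Kaplan-Meier curve needs groups that are known at time zero. I3 is known only when observation ends. That suits an incidence count, where each patient must appear once under his worst confirmed class. It does not suit a curve that starts when ITI starts.

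The bias arises because a patient who succeeds early completes the study and can no longer be reclassified. A patient who is reclassified must have been without success up to the rise. I3 takes that success-free time out of the low-titre curve and puts it into the high-titre curve. The low curve then describes patients selected for a favourable course, and the two curves separate even if titre at ITI start is irrelevant. A reader who takes the curves as prognosis by starting titre would be misled.

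**Working it through.** **1. Is there a figure to reproduce?** No. The documents give no expected ITI success rate, titre-rise rate or number of ITI patients for this output. All rates below are assumptions.

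**2. Could I3 move patients after ITI starts?** Yes. ITI lies inside the observation period (protocol 6.1.2, 6.2.2), central titres are planned on ITI (Table 8), and a rise to 5 BU or more is foreseen (protocol 5.4). Table 5 also places an optional epitope sample just after the peak titre during ITI, so a peak after time zero is expected in some patients.

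**3. Model.** Half of ITI patients start below 5 BU. Success has the same constant hazard λ in all patients. Low starters have rise hazard μ, and a rise counts only before success and does not change prognosis. Follow-up ends at 36 months, the protocol's maximum ITI length. The true gap is therefore 0.
- True success by t: F(t) = 1 − e^(−λt)
- Success by t with no earlier rise: L(t) = λ/(λ+μ) × [1 − e^(−(λ+μ)t)]
- Share of low starters who stay low: P = L(36) + e^(−36(λ+μ))
- Low curve under I3: L(t)/P
- High curve under I3: [2F(t) − L(t)]/(2 − P)

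**4. Middle case** (36-month success 70%, latent rise 25% over 36 months).
- λ = −ln(0.30)/36 = 0.0334; μ = −ln(0.75)/36 = 0.0080
- L(12) = 0.807 × (1 − 0.608) = 0.316; L(36) = 0.807 × (1 − 0.225) = 0.6255
- P = 0.6255 + 0.225 = 0.8505, so 15% of low starters are reclassified
- 12 months: low 0.316/0.8505 = 37.2%; high (0.661 − 0.316)/1.1495 = 30.0%; true 33.1% in both
- 36 months: low 73.5%; high (1.400 − 0.6255)/1.1495 = 67.4%; true 70.0% in both

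A simulation of 1,000,000 patients agrees: 37.1% vs 29.9% at 12 months and 73.4% vs 67.3% at 36 months.

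**5. Early rises only** (median time to success 9 months; 20% latent rise by 3 months, none later).
- λ = ln 2/9 = 0.0770; μ = −ln(0.80)/3 = 0.0744 up to month 3
- L(3) = 0.5087 × (1 − 0.635) = 0.1857
- L(12) = 0.1857 + 0.80 × (0.7937 − 0.3969) = 0.5032
- P = 0.1857 + 0.80 × 0.7937 = 0.8207
- 12 months: low 61.3%, high 0.7031/1.1793 = 59.6%, true 60.3%. The false gap is 1.7 points. Letting response vary between patients (log-SD 0.8) raises it only to about 2.

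**6. Range.** The simulation was repeated with 36-month success of 50%, 70% or 85% and latent rise of 10%, 25% or 40%, within 6 or within 36 months.

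| Grouping | Low minus high, 12 months | Low minus high, 36 months |
|---|---|---|
| Class at ITI start | 0 (simulation error at most 0.3) | 0 (simulation error at most 0.3) |
| Final class (I3) | 0.9 to 11.8 points | 0.5 to 11.4 points |

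If a rise instead halves the later success hazard, the I3 gap at 12 months is 1.5 to 13.1 points in favour of low titre. By class at ITI start, low starters are then slightly worse (0.1 to 6.0 points), because the model lets only them rise.

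**7. Small numbers** (assumed). Ten low and ten high starters have 7 successes each. Three low starters rise, and one of these succeeds. Under I3, 7/10 vs 7/10 becomes 6/7 (86%) vs 8/13 (62%).

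**The case against.** **The link to I3 is an inference.** The figure row does not cite I1-I3, the SAP does not define the observation period, and it speaks in places of a main study and an ITI study. This is fair, but no other class rule exists and the protocol carries observation through ITI. If I3 was not meant, the strata are undefined and the same sentence is needed.

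**The output is peripheral.** ITI success is not among the protocol's objectives, and all analyses are descriptive. With inhibitors in up to about 30% of 100 patients (protocol 1.1), an even split gives at most about 15 per curve. At 60% success the standard error of a difference is √(2 × 0.6 × 0.4/15) = 0.18, or 18 points, so a shift of a few points would not be visible as such. This stands and limits the weight of the point. It does not justify a grouping known to push in one direction.

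**No contrast is planned.** SAP 9.6 promises a distribution, not a low-versus-high comparison, and curves labelled by final class would be legitimate description. That is true, but no such label is planned, and side-by-side curves by titre invite a prognostic reading.

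**Risers can be traced.** Listings 16.2.8.2 and 16.2.8.4 and Table 14.2.10 would let a reader find them. That helps a careful reader but leaves the figure as it is.

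**A stronger reading.** A reader might infer a very large distortion. If the rise rate in step 5 continued for 36 months, I3 would show 83% vs 52% at 12 months. That requires 1 − 0.80^12 = 93% of low starters to have a latent rise, with about 49% actually reclassified. Nothing in the documents supports such a constant rate.

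**Conclusion.** The point holds as a bias of known direction and unknown size. Applying the SAP's only class rule to Figure 14.2.14 makes the low-titre curve too favourable and the high-titre curve too unfavourable. Where a rise does not change prognosis, the false gap at 12 months is about 1 to 12 points over the rates tried, and under 2 points if rises are few and confined to the first 3 months. It is larger only if rises continue at a high constant rate. These figures rest on assumed success and rise rates and on equal numbers of low and high starters.

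Only a confirmed central-laboratory rise or a data review decision moves a patient; a single unconfirmed high value does not. It would be wrong to infer that the inhibitor incidence results are biased by this. The primary endpoint and the any-inhibitor ITI curve do not depend on the low/high split, and I3 is suitable for counting incidence by class.

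**What to change.** In SAP 9.6 and the row for Figure 14.2.14:
- Start the time axis at the first ITI dose.
- Classify each ITI patient by the peak central-laboratory titre in samples drawn up to that dose (<5 or ≥5 BU).
- Allow a pre-ITI value ≥5 BU to be confirmed by retest of that sample or by a later sample, as I1 does. Otherwise a patient first found high just before ITI would be misclassified or left without a class.
- List confirmed rises to ≥5 BU on ITI within the starting group.
- Keep I3 for the incidence analyses.

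Using the last rather than the peak pre-ITI titre would also remove the bias; the choice should be stated in advance.

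**Cost.** A short addition to SAP 9.6 and a relabelled figure. No new data are needed, because Table 5 already schedules an inhibitor level before ITI. The downside is a footnote where a patient's ITI class differs from his incidence class. No change to treatment is implied.
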